7.5.1 Adverse Events

The coding dictionary for this study will be MedDRA v23.0. Treatment-emergent AEs will be coded to SOC and preferred terms using MedDRA and graded using NCI-CTCAE v4.03.

Treatment-emergent AEs will be tabulated alphabetically by SOC and by preferred terms within SOC.

An overview table will include the following details per treatment group and overall:

- Number of TEAEs,
- Number and percentage of patients with TEAEs,
- Number of NCI-CTC grades 3 and 4 TEAEs,
- Number and percentage of patients with NCI-CTC grades 3 and 4 TEAEs,
- Number of drug related NCI-CTC grades 3 and 4 TEAEs,
- Number and percentage of patients with drug related NCI-CTC grades 3 and 4 TEAEs,
- Number of drug related TEAEs,
- Number and percentage of patients with causally drug related TEAEs,
- Number of serious TEAEs,
- Number and percentage of patients with serious TEAEs,
- Number of serious drug related TEAEs,
- Number and percentage of patients with serious drug related TEAEs,
- Number of TEAEs leading to death,

- Number and percentage of patients with TEAEs leading to death,
- Number of drug related TEAEs leading to death,
- Number and percentage of patients with drug related TEAEs leading to death,
- Number of TEAEs leading to withdrawal of treatment,
- Number and percentage of patients with TEAEs leading to withdrawal of treatment,
- Number of TEAEs leading to dose reduction,
- Number and percentage of patients with TEAEs leading to dose reduction,
- Number of TEAEs leading to dose interruption,
- Number and percentage of patients with TEAEs leading to dose interruption,
- Number of drug related TEAEs leading to withdrawal of treatment,
- Number and percentage of patients with drug related TEAEs leading to withdrawal of treatment.

An overview table of the TEAE of interest will describe by the number and percentage of patients with TEAEs of interest per treatment group and overall.

The number and percentage of patients with TEAEs, as classified by SOC and preferred terms will be summarized for each treatment group and overall. Summaries will be provided for:

- TEAEs
- NCI-CTC grade 3 or higher TEAEs
- drug related NCI-CTC grade 3 or higher TEAE
- drug related TEAEs,
- serious TEAEs,
- drug related serious TEAEs,
- TEAEs leading to withdrawal of treatment,
- TEAEs leading to dose reduction,
- TEAEs leading to dose interruption,
- drug related TEAEs leading to withdrawal of treatment,
- TEAEs, excluding serious AEs, that equal to or exceed a threshold of 5.0% in any treatment group,
- TEAEs leading to death,
- drug related TEAEs leading to death,

The number and percentage of patients with TEAEs, classified by preferred terms by decreasing frequency within the overall group will also be summarized.

The number and percentage of patients with TEAEs that equal to or exceed a threshold of 5.0% in any treatment group, classified by preferred terms by decreasing frequency within the overall group, on a 6 monthly basis (0- <3 months; 3- <6 months; 6- <12 months; 12 months or more). The percentage of patients are calculated based on the number of patients still on treatment at the time point corresponding to the lower limit of the time intervals.

To adjust for the treatment duration, the number of TEAEs per 100 patients-years will be summarized, as classified by SOC and PT, per treatment group and overall. The number of TEAEs per 100 patients-years is calculated as the number of events *100 / (sum of the

treatment emergent period duration of all patients treated in the corresponding treatment group, in years).

The number and percentage of patients with TEAEs, as classified by SOC and preferred terms will also be summarized by maximum severity (reported according to NCI- CTCAE version 4.03).

In the patient count, if a patient has multiple TEAEs with the same SOC or PT, but with different severity, then the patient will be counted only once with the worst severity. However, if any of the severity values are missing then the patient will be counted only once with missing severity. In the AE count, the AEs will be presented in each category they were classified to. An AE can be reported multiple times in the AE module if its toxicity grade changes. Summaries will be provided for:

- TEAEs by NCI- CTCAE
- drug related TEAEs by NCI- CTCAE,
- serious TEAEs by NCI- CTCAE

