### **2.3.4 Safety Endpoints**

- Nature, frequency and severity of AEs
- Safety laboratory tests: biochemistry and hematology
- Physical examination
- ECG
- Vital signs (blood pressure, pulse and temperature)

- CONFIDENTIAL -

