### **5.5.1.3 Disease Progression and Study Endpoints**

Under this protocol, the following event(s) will not be considered as an(S)AE:

- Disease Progression: events including defined study endpoints that are clearly consistent with the expected pattern of progression of the underlying disease are not to be recorded as AEs. These data will be captured as efficacy assessment data as outlined in [Section 5.3](#). If there is any uncertainty as to whether an event is due to anticipated disease progression and/or if there is evidence suggesting a causal relationship between the study drug and the event, it should be reported as an (S)AE. All deaths up to 30 days after the last dose of study drug must be reported as an SAE, even if attributed to disease progression. And this event is recorded as an SAE with 'disease progression' as the reported term.
- Pre-planned and elective hospitalizations or procedures for diagnostic, therapeutic, or surgical procedures for a pre-existing condition that did not worsen during the course of the clinical trial. These procedures are collected per the eCRFs Completion Guidelines.

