6.2 Safety Variables

Safety will be assessed by evaluation of the following variables:

- Treatment-emergent AEs (TEAEs; frequency, severity, seriousness, and relationship to study drug).
- Clinical laboratory variables (hematology, biochemistry, PSA and testosterone)
- Vital signs (systolic and diastolic blood pressure and pulse rate) and weight
- 12-lead ECG

Treatment-Emergent Adverse Event (TEAE)

A TEAE is defined as an AE that occurs or worsens at any time during the treatment emergent period. The treatment emergent period for double-blind treatment period is defined as the time interval from the first study drug intake up to 30 days after the date of the last dose of study drug, study discontinuation, the start of new antineoplastic therapy or prior to first open-label treatment, whichever occurs first. The treatment emergent period for open-label phase is defined as the time interval from the first open-label study drug intake up to 30 days after the date of the last dose of study drug, study discontinuation or the start of new antineoplastic therapy, whichever occurs first.

If AE start date is the same date as the study start, then it will be considered as a TEAE if the box '*Onset after first dose of study drug taken*' is ticked in the Electronic case report form(eCRF). If a patient experiences an event both during the pre-investigational period and during the investigational period, the event will be considered as TEAE only if it has worsened in severity (i.e. it is reported with a new start date and an increased NCI-CTCAE grade).

AE with both a missing start and stop dates, and AEs with a missing start date but has a known stop date which is on or after the first dose of study drug will be considered treatment-emergent.

AEs will be coded to SOC and preferred term using MedDRA v23.0 (or later version) and severity graded using National Cancer Institute's Common Terminology Criteria version 4.03 (NCI-CTCAE v4.03) for AEs.

Drug-Related TEAE

A drug related TEAE is defined as any TEAE with a causal relationship to study drug as assessed by the investigator in the eCRF (by answering 'YES') or with missing assessment of the causal relationship.

AEs of Special Interest

AEs of special interest are defined in Table 7

Table 7 Selection Criteria for AEs of Special Interest

Event of special interest	Selection based on MedDRA 23.0
Convulsion	Narrow SMQ of 'Convulsions'
Hypertension	Narrow SMQ 'Hypertension'

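### Progression deaths enter the serious, fatal and grade 3-or-higher TEAE counts with no separate rows, and the SAP's severe-event definitions do not reconcile; temperature is also left out

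*SAP*

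**What the plan says.** **Progression deaths.** Protocol 5.5.1.3 keeps ordinary disease progression out of the adverse-event data but makes an exception for death: "All deaths up to 30 days after the last dose of study drug must be reported as an SAE, even if attributed to disease progression". It adds that "this event is recorded as an SAE with 'disease progression' as the reported term".

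**Window.** SAP 6.2 runs the double-blind treatment-emergent period from first dose to 30 days after last dose. It closes earlier at study discontinuation, new antineoplastic therapy or the start of open-label drug.

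**Overview table, SAP 7.5.1.** The rows include patients with serious TEAEs and "Number and percentage of patients with TEAEs leading to death". Neither has a version that sets the progression term apart. Four lines describe severe events: event counts and patient counts, each for all-cause and for drug-related TEAEs. The all-cause patient line is "Number and percentage of patients with NCI-CTC grades 3 and 4 TEAEs".

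**SOC/PT tables, same section.** The severe-event summary is "NCI-CTC grade 3 or higher TEAEs", with a matching drug-related table. Fatal and serious TEAEs are also tabulated by SOC and preferred term.

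**Vital signs.** Protocol 2.3.4 lists "Vital signs (blood pressure, pulse and temperature" among the safety endpoints, and Protocol 7.5.3 plans a summary of each vital sign at each time point. SAP 6.2 lists "Vital signs (systolic and diastolic blood pressure and pulse rate) and weight", and SAP 7.5.3 summarises the same set.

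**The concern.** The trial tests whether enzalutamide delays progression. Deaths attributed to progression are an outcome of the disease, yet they sit in the same all-cause rows as toxicity. If their frequency differs between arms, the serious and grade 3-or-higher contrasts contain an efficacy component that a reader of the summary tables cannot remove.

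The second issue is internal consistency. The overview and the SOC/PT tables beneath it give severe-event totals under different definitions, so the two patient counts need not agree and the reader is not told why.

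The third is simply that a protocol safety endpoint has no planned summary. It has no bearing on the other two.

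**Working it through.** No figure in the documents is in dispute, so the check compares definitions and adds some illustrative arithmetic. The planned arms of 120 and 60 (SAP 4) serve as approximate denominators.

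**1. Which rows are affected.** A progression death inside the window is serious by Protocol 5.5.1.3 and is fatal. It is grade 3 or higher on the assumption that it is graded 5, in line with the death category in Protocol 5.5.4. It enters the drug-related rows only if the investigator judges it related or causality is missing (SAP 6.2). Those rows are therefore largely unaffected.

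**2. What can be recovered by subtraction.** For one arm, let N be the patients with at least one qualifying TEAE, D the patients with a progression death, and B those among D who also have another qualifying TEAE. Then

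patients excluding progression deaths = N − (D − B).

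- *Fatal.* A patient dies once and the reported term is fixed, so B is normally 0. The answer is N − D, and D can be read from the preferred-term table.
- *Serious and grade 3 or higher.* A patient who dies of progression may well have had another serious or severe event. B is in no planned summary. The tables show only that the answer lies between N − D and N. With D = 3, for example, that interval is 3/120 = 2.50 points wide on enzalutamide and 3/60 = 5.00 points wide on placebo.

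**3. Possible shift between arms (assumed rates only).** The documents give no rate of progression death in the window. The shift in the enzalutamide-minus-placebo difference in fatal TEAEs equals the difference in progression-death rates:

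| Assumed rates, enzalutamide vs placebo | Patients | Shift |
|---|---|---|
| 1% vs 2% | 1.2 vs 1.2 | −1 point |
| 2% vs 4% | 2.4 vs 2.4 | −2 points |
| 5% vs 10% | 6 vs 6 | −5 points |
| Equal rates | – | 0 |

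If the rates were reversed, the sign would reverse. For serious TEAEs the shift contributed by each arm is (D − B)/n, which is at most D/n.

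**4. Overview against SOC/PT table.** The grade 3-or-higher count minus the grades 3-and-4 count is the number of patients whose only grade 3-or-higher TEAE is grade 5. Each such patient opens a gap of 1/120 = 0.83 points on enzalutamide or 1/60 = 1.67 points on placebo. A patient whose fatal event was also entered earlier at grade 3 or 4 opens no gap, because SAP 7.5.1 allows an event to be reported again when its grade changes.

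**5. Temperature.** It appears in Protocol 2.3.4, is measured under Protocol 5.4.1 and falls under the each-vital-sign rule of Protocol 7.5.3. It is absent from SAP 6.2 and 7.5.3, and no reason is given.

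**The case against.** The case for leaving the tables alone has real content.

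- Counting all on-treatment deaths whatever their attribution is a legitimate choice. An exclusion depends on the investigator's judgement of cause. This stands, and it is why the extra rows should sit beside the all-cause rows.
- A reader might infer that the tables hide an excess of non-progression deaths on enzalutamide. They do not. Fatal TEAEs are tabulated by preferred term and by arm, there are drug-related versions, and SAP 7.5 lists all adverse events.
- A reader might also infer that the drug will look safer merely because it delays progression. The documents do not establish that direction. The window closes at new therapy or open-label start, entry requires ECOG 0 or 1 and an expected survival of at least 12 months, and longer time at risk on enzalutamide could push crude percentages the other way.
- It is tempting to say that grade 5 events are lost from the overview, or that the SAP departs from the protocol. Neither is so. The overview has its own fatal rows, and grades 3 and 4 is the wording of Protocol 7.5.
- The grades 3-and-4 lines already keep out progression deaths graded 5, and widening them brings those deaths in. This stands, and it means the wording change and the rows excluding the term should be made together.
- Safety is descriptive, with no test or decision rule attached. Temperature values would still appear in the listing of vital signs, and clinically significant abnormalities become adverse events.

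Two things are left unanswered. The serious and grade 3-or-higher patient totals without progression deaths are not available from any planned summary, and the two severe-event definitions sit in one section without explanation.

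**Conclusion.** The point holds as a low-cost improvement to the safety tables. It does not touch the primary analysis.

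- All-cause serious, fatal and grade 3-or-higher counts include progression deaths within the TEAE window. The fatal count can normally be separated from the planned preferred-term table. The other two patient totals cannot be recovered from the planned summaries, although a hand count from the listings would be possible.
- Neither the size nor the direction of any shift between arms is documented. The range of −1 to −5 points rests wholly on assumed progression-death rates of 1% vs 2% up to 5% vs 10%. It should not be read as evidence of masking.
- The overview and SOC/PT severe counts differ by 0.83 points (of 120) or 1.67 points (of 60) for each patient whose only severe TEAE is grade 5. This is a mismatch inside the SAP.
- The omission of temperature is real, minor and separate.

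**What to change.** 1. In SAP 7.5.1 keep the all-TEAE rows as they are. Add patient counts for serious, fatal and grade 3-or-higher TEAEs that exclude the reported term disease progression. State that the exclusion relies on investigator attribution and supplements the all-cause rows.
2. In the four severe-event lines of the overview, use grade 3 or higher so that they reconcile with the SOC/PT tables.
3. Add temperature to SAP 6.2 and 7.5.3.

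The data are already collected, and Protocol 5.5.1.3 fixes the reported term, so the exclusion is a simple filter. The cost is a wording revision, which SAP 1 permits before database hard lock, and a few extra table rows.

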Study drug therapy should be continued as long as the subject is tolerating the study drug and continues ADT until radiographic disease progression is documented as outlined in table 3 or starting another investigational agent or new therapy for treatment of prostate cancer. It is recommended that subjects remain on study treatment until confirmed radiographic disease progression. Subjects who discontinue study treatment without confirmed radiographic disease progression will continue to follow the PSA and radiographic assessment schedule until confirmed radiographic disease progression event. In the judgment of the Investigator, for subjects who discontinue study treatment with confirmed PSA progression by central review, blinding suggests to be continued until confirmed radiographic disease progression. In consultation with the medical monitor, unblinding of the study treatment assignment may be performed after radiographic progression if the subject discontinues from the study treatment and in the judgement of the investigator this information is necessary to determine the next course of therapy. Open-label enzalutamide will be supplied for free to the subjects in placebo arm who remain on study treatment until confirmed radiographic disease progression and in the judgement of the investigator who is necessary to initiate the next course of therapy till next disease progression based on the subject's informed consent.

Study films (CT/MRI and bone scan) should be read on site and also be submitted in digital format to the sponsor-designated facility in case independent central review is required after the end of study. Each site should ideally designate the same reader who will evaluate the images for any one subject for the duration of the trial.

Radiographic disease progression is defined by Response Evaluation Criteria in Solid Tumors (RECIST) version 1.1 for soft tissue disease or the appearance of 2 or more new lesions on bone scan. The documentation and confirmation required for the determination of radiographic progression is listed in full protocol [Section 5.3.1.2 CT/MRI and Bone Scan].

The following assessments of prostate cancer status will be collected during the course of the study: PSA, soft tissue disease on CT scan or on MRI, bone disease on radionuclide bone scans, EQ-5D-5L, QLQ-PR25, FACT-P for QoL and BPI-SF for pain symptom assessment.

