Second primary malignancies	
Narrow SMQs of 'Malignant or unspecified tumours' customized to exclude preferred terms of 'Congenital fibrosarcoma', 'Congenital malignant neoplasm', 'Congenital retinoblastoma', 'Metastases to...', 'Metastasis', 'Metastatic neoplasm', 'Prostate cancer...', 'Carcinoid tumour of the prostate', and 'Neoplasm prostate'
 
AND (inclusive of)
 
Narrow SMQ of 'Myelodysplastic syndrome'
 
AND (inclusive of)
 
All preferred terms under High Level Term of 'Myeloproliferative disorders (excl leukaemias)'
 
 Note: Non-melanoma skin cancers are excluded (preferred terms of 'Basal cell carcinoma', 'Basosquamous carcinoma', 'Basosquamous carcinoma of skin', 'Keratoacanthoma', 'Skin cancer', 'Skin cancer metastatic', 'Squamous cell carcinoma', 'Squamous cell carcinoma of skin', 'Lip squamous cell carcinoma')
 
 Note: Those selected SPM cases will be adjudicated by medical review, which will confirm the evidence of a second primary malignancy

Note: Second primary malignancy reported as TEAEs of special interest will be presented for the entire duration of the study, not merely for the treatment-emergent period.

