7 STATISTICAL METHODOLOGY

7.1 General Considerations

For continuous variables, descriptive statistics will include the number of patients (n), mean, standard deviation, median, minimum and maximum. When needed, the use of other percentiles (e.g.10%, 25%, 75% and 90%) will be mentioned in the relevant section.

Frequencies and percentages will be displayed for categorical data. Unless otherwise specified, percentages by categories will be based on the number of patients with no missing data, i.e. will add up to 100%.

All summary tables and figures will be presented by treatment arm and overall for double-blind treatment period, unless stated otherwise. For open-label phase, only selected summaries will be presented , the titles of selected tables, listings and figures for open-label phase summaries will be written out to indicate the “Open-label Phase”, refer to Appendix 3 for detailed analyses for open-label phase. All listings will be produced by site and patient id numbers in ascending order.

Disposition, demographics and other baseline characteristics as well as efficacy data will summarized based on the ITT population, unless stated otherwise. Safety analysis summary and other summaries based on SAF are presented by actual treatment received, unless stated otherwise.

All statistical comparisons will be made using two sided tests comparing double-blind enzalutamide to double-blind placebo. All null hypotheses will be of no treatment difference. All analyses will be based on IRT captured strata. Multiplicity adjustment was incorporated within the interim and final analysis of the primary endpoint according to the O’Brien-Fleming method with a Lan-DeMets alpha spending function (refer to Section 6.1.1.1). And no adjustment for multiplicity will be made for this study on the other endpoints, hence any p-values displayed for those endpoints are intended to be read descriptively.

All data processing, summarization, and analyses will be performed using SAS® Version 9.1.3 or higher. Specifications for table, figures, and data listing formats can be found in the TLF specifications for this study.

For the definition of subgroups of interest, please refer to Section 7.9.

A data analysis cut-off date for the database will be used. All data from visits or assessments done prior to the cut-off date will be reported.

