7.3 Study Drugs

7.3.1 Exposure

The following information on drug exposure will be presented for each treatment group for the SAF:

- The duration of exposure (number of months) to study medication will be summarized using descriptive statistics, including 10%, 25%, 75% and 90% percentiles.
- Number and percentage of patients on study drug at 6 months and at year 1, 2, 3, and 4 (that is with duration of exposure superior or equal to day 182, 365, 730, 1095, and 1461).
- Number and percent of patient with dose reductions, increases or interruptions, the reasons for these, as well as the number of these per patient.
- Descriptive statistics for the total dose and the average daily dose of the drug patient was exposed to.

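### The 15 multi-term special-interest groups get only crude patient percentages; a first-event rate per 100 patient-years beside them would be a cheap, minor improvement

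*SAP*

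**What the plan says.** SAP 6.2, Table 7, defines 17 special-interest groups. SAP 7.5.1 plans one summary at that level: "An overview table of the TEAE of interest will describe by the number and percentage of patients with TEAEs of interest per treatment group". The same figures are given for both arms combined.

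Two other outputs in SAP 7.5.1 deal with time on treatment:

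- A rate table: "To adjust for the treatment duration, the number of TEAEs per 100 patients-years will be summarized, as classified by SOC and PT". Its numerator is the number of events, and its denominator is the arm's summed treatment-emergent time.
- An interval table of patients with common TEAEs, over 0 to <3, 3 to <6, 6 to <12 and 12 or more months. It is by preferred term, only for terms reaching 5.0% in either arm, with percentages "calculated based on the number of patients still on treatment at the time point corresponding to the lower limit of the time intervals".

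For the double-blind period, SAP 6.2 counts events over "the time interval from the first study drug intake up to 30 days after the date of the last dose of study drug", cut short by study discontinuation, new antineoplastic therapy or the first open-label dose. Second primary malignancies are an exception: they "will be presented for the entire duration of the study, not merely for the treatment-emergent period".

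SAP 7.3.1 summarises exposure by arm, including "Number and percentage of patients on study drug at 6 months and at year 1, 2, 3, and 4". SAP 7.1 places layouts in a document that was not supplied: "Specifications for table, figures, and data listing formats can be found in the TLF specifications for this study".

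**The concern.** SAP 3.2 says of study drug: "It is recommended that subjects remain on study treatment until confirmed radiographic disease progression". If enzalutamide delays progression, its patients will tend to be observed for longer within the treatment-emergent period. A crude percentage then rises with observation time even when the risk per month is the same in both arms.

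The sponsor treats this as relevant for the drug. Protocol 1.3 reports median exposure of 17.9 months on enzalutamide and 7.1 on placebo in the pooled phase 3 studies. It also notes that differences in common TEAEs shrank, vanished or reversed after adjustment for duration. Yet the groups singled out here for attention are the ones without a planned patient-level adjustment. What is at stake is how a descriptive safety table reads.

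**Working it through.** The plan gives no figure of its own on this point. The check is a count, a comparison of outputs, and an illustration.

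**Count.** Of the 17 groups in Table 7, Fall and posterior reversible encephalopathy syndrome are single preferred terms, so the PT table already gives each an event rate. The others combine terms through an SMQ, a high-level term or a list of PTs: 17 - 2 = 15.

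**What the two time-related outputs can supply for those 15.**

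- All PT event rates in an arm share one denominator, so they add up to a group event rate. That is not a rate of patients affected. One patient may have several terms or repeat events, and SAP 7.5.1 notes that an AE may be entered again when its toxicity grade changes, so the sum may be inflated.
- Interval percentages cannot be added over PTs, because patients overlap. The 5.0% threshold is 0.05 x 120 = 6 enzalutamide or 0.05 x 60 = 3 placebo patients; a term below both is left out.

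Neither protocol 7.5, 7.5.1 and 12.10.7 nor SAP Appendix 3 adds an exposure-adjusted summary for these groups.

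**Size, by illustration.** The documents give no exposure for this trial and no first-event rate for any group. Inputs:

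- 120 and 60 patients; uniform accrual over 15 months and 12 months of follow-up, so cut-off c = 27 months (protocol synopsis, sample size).
- Exponential time on drug with medians of 18 and 9 months (the planning medians for PSA progression, although drug continues past it), or 33.0 and 14.8 months (rPFS medians of another drug's trial, protocol 1.1). Both pairs are assumptions.
- A constant first-event rate r, equal in both arms: 2.0 (assumed), 5.4 or 8.1 per 100 patient-years. The last two are the pooled placebo and enzalutamide rates for hypertension as an individual TEAE (protocol 1.3). They may count repeats and so exceed a first-event rate.
- At-risk time = min(time on drug + 1 month, c - entry time). Earlier truncation at new therapy is ignored.

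With λ = r/1200 per month, the probability of a first event is P = λ ∫ G(t) H(t) exp(-λt) dt from 0 to c. Here G(t) = min(1, (c - t)/15); H(t) = 1 up to 1 month and 2^(-(t - 1)/median) after that.

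Mean treatment-emergent time at 27 months is 14.1 vs 10.7 months (18/9) or 16.2 vs 13.2 (33.0/14.8). Crude percentages, enzalutamide vs placebo:

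| Rate per 100 patient-years | Medians 18/9 | Excess (points) | Medians 33.0/14.8 | Excess (points) |
|---|---|---|---|---|
| 2.0 | 2.3 vs 1.8 | 0.5 | 2.7 vs 2.2 | 0.5 |
| 5.4 | 6.1 vs 4.7 | 1.4 | 7.0 vs 5.7 | 1.3 |
| 8.1 | 9.0 vs 6.9 | 2.1 | 10.3 vs 8.4 | 1.9 |

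Over assumed cut-offs of 20 to 40 months, the excess is 0.2 to 1.1, 0.6 to 2.7 and 0.9 to 3.9 points for the three rates. The crude ratio runs from 1.14 to 1.49. The excess grows with a later cut-off and is zero if exposure is equal.

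**Against sampling error** (27 months, 18/9, rate 8.1). SE = sqrt(0.090 x 0.910/120 + 0.069 x 0.931/60) = 0.042. The difference is 2.1 points with approximate 95% limits of 2.1 ± 8.2, or -6 to +10.

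**What a first-event rate does.** In that case 10.7 and 4.1 first events are expected on 133 and 51 patient-years at risk. Both give about 8 per 100, so the shift is gone.

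**The case against.** The strongest reply is that duration is already handled and that a reader can build the missing figure. Much of this stands. PT rates can be added to a group event rate. A close patient-level rate also follows from planned tables: patients affected, divided by n times mean exposure, since SAP 7.1 includes n and mean in its descriptive statistics and the treatment-emergent period adds up to 30 days per patient. Using total treatment-emergent time in the illustration, 10.7/(120 x 14.1/12) = 7.6 and 4.1/(60 x 10.7/12) = 7.7 per 100 patient-years. The ratio is 0.99, against a crude ratio of 1.30; over all the scenarios it is 0.98 to 1.00. So a reader might infer that no adjusted group figure can be obtained, and the documents do not support that. What is missing is a direct, reported figure with its interval.

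The effect is also small and rests on assumed inputs, all AEs are listed (SAP 7.5), and the TLF specifications may already contain the row. All of this stands. It limits the weight of the point without removing the gap in the text.

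It is also tempting to ask for a whole-study rate for second primary malignancies, since Table 7 counts them for the whole study. The documents do not support that denominator. Protocol 5.5.1 and 5.5.5 end general AE collection at the earlier of 30 days after the last dose (open-label dosing included) and new prostate cancer therapy. Post-treatment follow-up then requires only symptomatic skeletal events. Under 5.5.6, later events must be notified only if possibly related to study drug or participation. Whole-study time would add follow-up without systematic collection. Under protocol 2.2.1 and 12.10, placebo subjects may also cross over to enzalutamide, so their later time would mix treatments.

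**Conclusion.** The point holds as a minor one. For 15 of the 17 groups the plan reports crude patient percentages and no direct exposure-adjusted patient-level figure. Some excess at equal risk will appear if enzalutamide patients stay on drug longer. In the illustration it is about 0.5 to 2.1 percentage points at 27 months and at most 3.9 points at 40 months. This rests on assumed exposure, constant equal first-event rates, and the absence of such a row in the TLF specifications; if those already contain it, the point falls away.

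A reader might infer from the pooled exposures of 17.9 and 7.1 months that crude percentages would more than double. With every patient exposed for exactly those times, a rate of 5 per 100 patient-years gives 1 - exp(-0.05 x 17.9/12) = 7.2% against 1 - exp(-0.05 x 7.1/12) = 2.9%, a ratio of 2.47. The documents do not support carrying this over: four of the five pooled studies were in castration-resistant disease, and this trial's exposure is unknown.

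Nor does the gap threaten a trial conclusion. The table is descriptive, with no test or decision rule attached, and SAP 7.3.1 would make an exposure imbalance visible.

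**What to change.** In SAP 7.5.1, add to the special-interest overview table, for each Table 7 group and arm, the number of patients with a first treatment-emergent event per 100 patient-years at risk, with an exact 95% CI. Time at risk runs from first dose to the first event in the group or the end of the double-blind treatment-emergent period. Keep the crude number and percentage beside it.

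For second primary malignancies, give this rate only for events in the treatment-emergent period. Keep the whole-study figure as a count and percentage, without a whole-study person-time denominator.

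The cost is a little programming on data already collected. Intervals will be wide: on 51 placebo patient-years, 4 first events give 7.8 per 100 (exact 95% CI 2.1 to 20.1) and 1 gives 2.0 (0.05 to 10.9). With 10.7 and 4.1 expected events, a rate ratio of 1.00 has approximate limits exp(±1.96 x sqrt(1/10.7 + 1/4.1)) = 0.32 to 3.1. With 7.3 and 2.8 events (rate 5.4) they are 0.25 to 4.0. The row removes the observation-time shift but adds no precision. If events cluster early, a patient-year rate favours the longer-observed arm, which is why both figures should be shown.
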